#### 22.1.3 End of Treatment and Follow-Up Tumor Imaging

For participants who discontinue study treatment, tumor imaging should be performed at the time of treatment discontinuation (±4 week window). If previous imaging was obtained within 4 weeks prior to the date of discontinuation, then imaging at treatment discontinuation is not mandatory. For participants who discontinue study treatment due to documented disease progression, this is the final required tumor imaging if the investigator elects not to implement iRECIST.

For participants who discontinue study treatment without documented disease progression, every effort should be made to continue monitoring disease status by tumor imaging using the same imaging schedule used while on treatment (every 9 weeks) until the start of a new anticancer treatment, disease progression, pregnancy, death, withdrawal of consent, or the end of the study, whichever occurs first.

#### 22.2 RECIST 1.1 Assessment of Disease

RECIST 1.1 will be used by the blinded, independent central reviewers (BICR) as the primary measure for assessment of tumor response, date of disease progression, and as a basis for all protocol guidelines related to disease status (e.g., discontinuation of study treatment).

All efficacy endpoints, including the primary response endpoint of Part 2, overall response rate within the first 24 weeks of treatment (ORR24), will be evaluated and categorized using the new international criteria proposed by the Response Evaluation Criteria in Solid Tumors (RECIST) Committee, version 1.1.

RECIST v1.1 response definitions are briefly described below; for detailed instructions on RECIST v1.1, please refer to Appendix 5.

RECIST v1.1 Response Definitions for the Evaluation of Target Lesions

Complete Response (CR)	Disappearance of all target lesions. Any pathological lymph nodes (whether target or non-target) must have reduction in short axis to < 10 mm.
Partial Response (PR)	At least a 30% decrease in the sum of diameters of target lesions, taking as reference the baseline sum diameters.
Progressive Disease (PD)	At least a 20% increase in the sum of diameters of target lesions, taking as reference the smallest sum on study (this includes the baseline sum if that is the smallest on study). In addition to the relative increase of 20%, the sum must also demonstrate an absolute increase of at least 5 mm. (Note: the appearance of one or more new lesions is also considered progression).

Stable Disease (SD)	Neither sufficient shrinkage to qualify for PR
	nor sufficient increase to qualify for PD,
	taking as reference the smallest sum
	diameters while on study.

RECIST v1.1 Response Definitions for the Evaluation of Non-Target Lesions

Complete Response (CR)	Disappearance of all non-target lesions and	
	normalization of tumor marker level	
Incomplete Response/Stable Disease (SD)	Persistence of one or more non-target	
	lesion(s) or/and maintenance of tumor	
	marker level above the normal limits	
Progressive Disease (PD)	Appearance of one or more new lesions	
	and/or unequivocal progression of existing	
	non-target lesions*	

\*Although a clear progression of "non target" lesions only is exceptional, in such circumstances, the opinion of the treating physician should prevail and the progression status should be confirmed later on by the review panel (or study chair)

RECIST v1.1 Definitions for the Evaluation of Overall Response

Target lesions	Non-Target lesions	New Lesions	Overall response
CR	CR	No	CR
CR	Incomplete response/SD	No	PR
PR	Non-PD	No	PR
SD	Non-PD	No	SD
PD	Any	Yes or No	PD
Any	PD	Yes or No	PD
Any	Any	Yes	PD

ORR is defined as the proportion of efficacy evaluable patients (see Section 24.3) with a tumor size reduction that meets the RECIST v1.1 Overall Response definition of a Partial Response (PR) or Complete Response (CR). If a CR has been confirmed for a patient, the sponsor will

discuss with the patient's investigator whether the study treatments need to be continued or not.

If a patient's responses could not be confirmed, that patient will not be included in the primary efficacy population for ORR24.

In addition, efficacy endpoints will also be determined using the immune-related RECIST (iRECIST) (please refer to Appendix 6).

#### 22.3 iRECIST Assessment of Disease

iRECIST is based on RECIST 1.1, but adapted to account for the unique tumor response seen with immunotherapeutic drugs. iRECIST will be used by the Investigator to assess tumor response and progression, and make treatment decisions. When clinically stable, participants should not be discontinued until progression is confirmed by the Investigator, working with local radiology, according to the rules outlined in Appendix 6. This allowance to continue treatment despite initial radiologic PD takes into account the observation that some participants can have a transient tumor flare in the first few months after the start of immunotherapy, and then experience subsequent disease response. This data will be captured in the clinical database.

Clinical stability is defined as the following:

- Absence of symptoms and signs indicating clinically significant progression of disease
- No decline in ECOG performance status
- No requirements for intensified management, including increased analgesia, radiation, or other palliative care

Any participant deemed **clinically unstable** should be discontinued from study treatment at site-assessed first radiologic evidence of PD, and is not required to have repeat tumor imaging for confirmation of PD by iRECIST.

If the Investigator decides to continue treatment, the participant may continue to receive study treatment and the tumor assessment should be repeated 4 to 8 weeks later to confirm PD by iRECIST, per Investigator assessment. Images should continue to be sent in to the central imaging vendor for potential retrospective BICR.

If repeat imaging does not confirm PD per iRECIST, as assessed by the Investigator, and the participant continues to be clinically stable, study treatment may continue and follow the regular imaging schedule. If PD is confirmed, participants will be discontinued from study treatment.

If a participant has confirmed radiographic progression (iCPD) as defined in Appendix 6, study treatment should be discontinued; however, if the participant is achieving a clinically meaningful benefit, an exception to continue study treatment may be considered following consultation with the Sponsor. In this case, if study treatment is continued, tumor imaging should continue to be performed following the intervals as outlined in the Schedule of Events (Appendix 1) and submitted to the central imaging vendor.

A description of the adaptations and iRECIST process is provided in Appendix 6, with additional details in the iRECIST publication. A summary of imaging and treatment requirements after first radiologic evidence of progression is provided in Table 6 and illustrated as a flowchart in Figure 5.

Table 6. Imaging and Treatment after First Radiologic Evidence of Progressive Disease

[figure not shown]
	Clinically Stable		Clinically Unstable	
	Imaging	Treatment	Imaging	Treatment
First radiologic evidence of PD by RECIST 1.1 [For those studies in which PFS is the primary endpoint, add the following: that has been verified by BICR]	Repeat imaging at 4 to 8 weeks to confirm PD.	May continue study treatment at the Investigator's discretion while awaiting confirmatory tumor imaging by site by iRECIST.	Repeat imaging at 4 to 8 weeks to confirm PD per Investigator's discretion only.	Discontinue treatment
Repeat tumor imaging confirms PD (iCPD) by iRECIST per Investigator assessment	No additional imaging required.	Discontinue treatment (exception is possible upon consultation with Sponsor).	No additional imaging required.	Not applicable
Repeat tumor imaging shows iUPD by iRECIST per Investigator assessment	Repeat imaging at 4 to 8 weeks to confirm PD. May occur at next regularly scheduled imaging visit.	Continue study treatment at the Investigator's discretion.	Repeat imaging at 4 to 8 weeks to confirm PD per Investigator's discretion only.	Discontinue treatment
Repeat tumor imaging shows iSD, iPR, or iCR by iRECIST per Investigator assessment.	Continue regularly scheduled imaging assessments.	Continue study treatment at the Investigator's discretion.	Continue regularly scheduled imaging assessments.	May restart study treatment if condition has improved and/or clinically stable per Investigator's discretion.  Next tumor imaging should occur according to the regular imaging schedule.

Clinically Stable		Clinically Unstable	
Imaging	Treatment	Imaging	Treatment

BICR = Blinded Independent Central Review; iCPD = iRECIST confirmed progressive disease; iCR = iRECIST complete response; iRECIST = modified Response Evaluation Criteria in Solid Tumors 1.1 for immune-based therapeutics; iSD = iRECIST stable disease; iUPD = iRECIST unconfirmed progressive disease; PD = progressive disease; RECIST 1.1 = Response Evaluation Criteria in Solid Tumors 1.1.; VOP=verification of progression

[For studies, in which PFS is the primary endpoint, add the following: Note: If progression has been centrally verified, further management is by the site, based on iRECIST. Any further imaging should still be submitted to the central imaging vendor, but no rapid review will occur. If RECIST 1.1 disease progression has not been centrally verified, ideally the site should continue treatment. Whether or not treatment continues, imaging should be collected and submitted to the central imaging vendor with VOP request until RECIST 1.1 progression is verified by BICR.]

Figure 5: Imaging and Treatment for Clinically Stable Participants Treated with pembrolizumab after First Radiologic Evidence of PD Assessed by the Investigator

#### 23.0 Correlative studies and biomarker evaluations

Establishing proof-of-biological concept is a key objective of this study. As previously described, the goal of GX-188E + P treatment is to induce a tumor-specific anti-tumor immunological response that does not become halted at the PD1 immune checkpoint. To explore the biological mechanisms and pharmacodynamic effects of the investigational treatment regimen, paired tumor biopsies and peripheral blood samples will be obtained from all study participants.

### 23.1 Tumor Tissue for Biomarker Analyses

A key exploratory objective of the study is to evaluate the additional immunological treatment effects of GX-188E + P on the tumor microenvironment depending on the PD-L1 expression at baseline. Tumor biopsy samples will be evaluated for molecular and histological changes, particularly as these changes pertain to the inflammatory mechanisms. This will be assessed by comparing paired biopsies whenever feasible, one obtained at baseline (archival or fresh sample) prior to study treatment initiation, and one obtained at approximately 10 weeks on study. The changes in the intratumoral inflammatory infiltrate and PD-L1 expression at baseline will be analyzed by immunohistochemical(IHC) staining and the tumor evaluation will be conducted by a central laboratory.

All patients must submit either an archival tumor tissue sample, or a fresh biopsy sample for biomarker testing, including staining for PD-L1. For this study, it is expected that archival tumor tissues will be the principal source for baseline tumor biomarker analysis. Patients who do not have either archival tumor tissues available or biopsy-accessible lesions for a fresh biopsy will be excluded from the study.

Ideally, archival samples should have been obtained within 30 days of study enrollment and without administration of other anti-cancer treatment(s) in the interim period. In cases where archival samples were obtained >30 days from study enrollment or other cancer treatments were administered in the interim, the biopsy date and interim cancer treatments should be documented.

For patients without archival tissue samples but who have biopsy-accessible lesions and agree to undergo a biopsy procedure, the baseline sample must be obtained prior to administration of the first dose of either GX-188E or pembrolizumab.

For patients with biopsy-accessible lesions, a second biopsy will be requested optionally approximately 10 weeks following study treatment initiation in order to evaluate the effects of the investigational treatment regimen on the tumor microenvironment. For patients who discontinue from study prior to Week 10 and with accessible lesions, every effort should be made to obtain an optional post-baseline biopsy. For detailed instructions on biopsy sample processing, please refer to the study Laboratory Manual.

Submission of formalin-fixed paraffin embedded tumor tissue sample blocks is preferred; if submitting unstained slides, the slides should be freshly cut and submitted to the testing laboratory otherwise a new specimen may be requested. For additional details on tissue sample submission, please refer to the study Laboratory Manual.

### 23.2 Planned Peripheral Blood Biomarker Analyses

All study participants are required to provide peripheral blood samples for exploratory immunological evaluation throughout their study participation according to the schedule described in the Schedule of Events (Appendix 1). In brief, peripheral blood samples will be obtained at Screening, Week 1, Week 4, Week 7, Week 10, Week 16, Week 22, Week 49, and approximately every 27 weeks thereafter. For detailed instructions on peripheral blood research sample processing, please refer to the study Laboratory Manual.

Peripheral blood samples will be evaluated for molecular markers of an antigen-specific cellular and humoral immune response. For example, paired pre- and post-baseline PMBC-derived T cells may be assessed for (1) increased HPV-specific T-cell responses by ELISPOT analysis; (2) modulation of T-cell receptor diversity; (3) epitope-spreading to non-HPV epitopes, including mutation-derived neoantigens; (4) multiparametric flow cytometry to assess additional leukocyte populations of immunologic interest.

#### 24.0 Statistical Analysis

#### 24.1 Statistical Plan Summary

Study Design Overview	This is a Phase Ib/II multicenter, open-label study in patients with advanced, non-
	resectable HPV 16 or 18-positive cervical cancer. The study consists of two different
	parts. Part A employs a standard 6 + 3 design to evaluate the safety of the
	investigational study regimen. Part B uses a Simon Two-Stage design to explore the
	efficacy of the investigational study regimen at the treatment schedule established as
	safe in Part A. Additional subjects will be enrolled in Part C to evaluate efficacy in
	larger population.

Analysis Populations	Safety Population: All patients who receive at least 1 dose of 1 agent in the investigational treatment regimen (i.e. either GX-188E or P) will be included in the analysis of safety, regardless of the duration of treatment.		
	DLT-evaluable Population . Part A patients who receive all of the planned administrations of both agents (GX-188E and P) within the DLT-evaluation period (the first three weeks of treatment prior to Week 4 Day 1 visit), unless doses are missed within the first two weeks of treatment (i.e., Week 1 Day -1 to Week 2 Day 7) due to DLT(s).		
	Efficacy Evaluable Population.		
	All patients who discontinue the study treatment regimen early due to treatment-related toxicity		
	
 
Patients who discontinue study due to disease-related death, unequivocal tumor progression or with at least 1 post-baseline tumor assessment AND who received at least 45 days of treatment
 
		
	
 
Patients from Part A, who receive the recommended Phase 2 regimen and who meet the aforementioned criteria
 
		
Primary Endpoint(s)	Part A: Safety: Incidence of Dose-limiting toxicities (DLTs) Part B&C: Objective Response Rate within 24 weeks (ORR 24 ) by RECIST 1.1. Response determinations from the BICR will be used for the primary endpoint		
Secondary Endpoints	
 
Incidence, nature and severity of adverse events and serious adverse events
 
Best Overall Response Rate (BORR), Time-to-Best Response (TTR), Duration of Response (DOR), Disease Control Rate (DCR), median Progression-Free Survival (mPFS) and 6 month PFS rate and Median Overall Survival(mOS)
 
Response endpoints by iRECIST
 
		
Statistical Methods for Efficacy & Immunogenicity/ Analyses	Efficacy Analyses. Descriptive statistics will be employed to analyze the efficacy data. It also provides subject plots for individual patients. Summary statistics for continuous variables will include the mean, standard deviation, median, interquartile range, and range (minimum/maximum). Categorical variables will be presented as frequency counts and percentages, and time-to-event variables will be summarized with number of non-missing observations, median survival time, and survival probability using Kaplan-Meier method if applicable. Kaplan Meier plot will also be provided.		
	Immunogenicity Analyses. Immunogenicity will be described to explore humoral and cellular immune responses to GX-188E and P (e.g., antibodies to E6 and E7 and the number of antigen-specific IFN-γ secreting T lymphocytes in samples of PBMC) in blood samples obtained from study subjects		
Treatment Assignment	All participants will be allocated GX-188E + pembrolizumab		
Statistical Methods for Safety Analyses	Summary statistics will be provided for the safety endpoints as appropriate.		
Interim Analyses	An interim analysis will be performed with safety and efficacy data in case of at least 22 patients in efficacy evaluable population, after obtaining week 10 tumor assessment results (either by investigator/BICR).		
Final Analysis	The final analysis will be performed to report a primary CSR based on a data cut off after all 60 patients in the planned efficacy evaluable population have completed tumor assessment within 24 weeks by the investigator per RECIST v1.1 Since patient will be treated until they met one of the discontinuation criteria, some patients may still be ongoing at the time of final analysis. Therefore, a long-term follow-up study can be performed after final analysis with all available data (no cut-off date applied).		
Multiplicity	No multiplicity adjustment is planned in this trial.		
Sample Size and Power	Part A Safety Evaluation: For Part A, the goal is to determine a treatment schedule for which the rate of DLTs is less than 33% in 6 or 9 patients. A minimum of 6 patients		

are planned with a maximum of 18 DLT-evaluable patients for the Starting Treatment Schedule and Reduction Level 1

**Part B:** Part B follows a 1-sided Simon 2-Stage design; 15 patients, will be included in the first stage analysis. If  $\geq 3$  objective responses (PR or better) are observed in the first stage, another 13 patients will be enrolled into the second stage, for a total of 28 patients. For a null hypothesis ORR24 of 0.15 and an alternative hypothesis ORR24 of 0.35, the sample size of 28 patients will provide a one-sided significance level of approximately 5% and a power of 80%.

**Part C:** Part C is to evaluate efficacy in larger patient population. In Keynote-158 study (pembrolizumab monotherapy in patients who have progressed with standard of care systemic therapy), ORR in total patients (i.e. regardless of PD-L1 status) and with CPS  $\geq 1$  were 12.2% and 14.6%, respectively. Given this, null hypothesis for ORR24 was set at  $P_0 = 12.2\%$ . With an alternative hypothesis for ORR24 of  $P_a = 37\%$ , the sample size of 60 subjects was calculated considering two-sided significance level of 0.05, 97% power, and 25% dropout rate. The confidence interval (CI) for ORR24 will be estimated using exact Clopper-Pearson method, and if the lower bound of the two-sided 95% CI for ORR24 exceeds 12.2%, it will be proven to satisfy the primary efficacy. And it will be analyzed using two-sided exact binomial test for a null hypothesis for ORR24 of  $P_0 = 12.2\%$  with a significance level of P < 0.05.

#### 24.2 General Statistical Considerations

This is a Phase Ib/II multicenter, open-label study in patients with advanced, non-resectable HPV 16 or 18-positive cervical cancer. The study consists of two different parts. Part A employs a standard 6 + 3 design to evaluate the safety of the investigational study regimen. Part B uses a Simon Two-Stage design to explore the efficacy of the investigational study regimen at the treatment schedule established as safe in Part A.

Since this is an open-label clinical trial, in general, descriptive statistics will be employed to analyze the data. Summary statistics for continuous variables will include the mean, standard deviation, median, interquartile range and range (minimum/maximum). Categorical variables will be presented as frequency counts and percentages, and time-to-event variables will be summarized with number of non-missing observations, median survival time, and survival probability using Kaplan-Meier method if applicable. Kaplan Meier plot will also be provided.

The data will be tabulated and analyzed with respect to patient enrollment and disposition, demographic and baseline characteristics, prior and concomitant medications, efficacy, and safety measures. The efficacy analysis will be conducted on the Efficacy Evaluable Population, and the safety analysis will be performed on the Safety Population.

All confidence intervals will be constructed at the 95% confidence level. Data listings will be created to support each table and to present all data collected.

In Part C, the significance level of 5% will be used for two-sided exact binomial test for a null hypothesis for  $ORR_{24}$  of  $P_0 = 12.2\%$ .

#### 24.3 Sample Size and Power

**Part A Safety Evaluation:** For the traditional 6+3 design of Part A, the goal is to determine a treatment schedule for which the rate of DLTs is less than 33% in 6 or 9 patients. A minimum of 6 patients are planned for Part A, with a maximum of 18 DLT-evaluable patients for the Starting Treatment Schedule and Reduction Level 1. If  $\geq$ 3 in 6 or 9 patients at Reduction Level 1 have DLTs, then the investigational treatment regimen will be considered too toxic and enrollment into the study will be discontinued.

Part B: Part B follows a 1-sided Simon 2-Stage design; 15 patients, including all patients from Part A without a DLT, who receive the recommended Phase 2 regimen and who meet the criteria for the Efficacy Evaluable Population (see Section 24.4), with HPV 16 or 18 positive advanced cervical cancer will be included in the first stage analysis. If 3 or more objective responses (PR or better) are observed in the first stage, another 13 patients will be enrolled into the second stage, for a total of 28 patients in Part B. Study has passed the first stage of Simon-Two stage design. For a null hypothesis ORR24 of 0.15 and an alternative hypothesis ORR24 of 0.35, the sample size of 28 patients will provide a one-sided significance level of approximately 5% and a power of 80%. If Stages 1 and 2 are completed, a minimum of 8 patients must demonstrate a response (PR or better) to reject the null hypothesis.

Part C: Part C is to evaluate efficacy in larger patient population. In Keynote-158 study (pembrolizumab monotherapy in patients who have progressed with standard of care systemic therapy), ORR in total patients (i.e. regardless of PD-L1 status) and with CPS  $\geq$  1 were 12.2% and 14.6%, respectively.

Given this, null hypothesis for  $ORR_{24}$  was set at  $P_0 = 12.2\%$ . With an alternative hypothesis for  $ORR_{24}$  of  $P_a = 37\%$ , the sample size of 60 subjects was calculated considering two-sided significance level of 0.05, 97% power, and 25% dropout rate.

The confidence interval (CI) for ORR24 will be estimated using exact Clopper-Pearson method, and if the lower bound of the two-sided 95% CI for ORR24 exceeds 12.2%, it will be proven to satisfy the primary efficacy.

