## **SAMPLE SIZE**

Approximately 46 patients will be enrolled and treated with the investigational combination in Parts A and B. It is expected that Part A will enroll between 6- and 18 patients, based upon the incidence of dose-limiting toxicities.

If at least 8 of the 28 subjects enrolled in Part B, experience an objective response who are considered to be evaluable for efficacy, it will be considered that ORR satisfies the criteria for study expansion and additional 17 subjects (at least) will be enrolled in Part C to evaluate efficacy further in larger population (N=60). Refer to the Section 24.3 Sample Size and Power for detailed assumptions for sample size estimation.

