# Part C. Efficacy Evaluation in Larger Number of Patients

If at least 8 of the 28 subjects enrolled in Part B, experience an objective response who are considered evaluable for efficacy, it will be considered that ORR satisfies the criteria for study expansion and additional 17 subjects (at least) will be enrolled in Part C to evaluate efficacy further in larger patient population (N=60). If only 7 or fewer subjects in Part B experience an objective response, enrollment to Part C will not open.

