## STATISTICAL METHODS

Maximum 60 patients are planned for enrollment into this clinical trial.

Safety Analysis. All patients who receive at least one dose of the investigational treatment will be included in the safety population. All safety analyses will be performed on the safety population. Adverse Events (AE) will be coded according to the MedDRA adverse event dictionary. The results will be tabulated to examine their frequency, organ systems affected, and relationship to study treatment. The results of laboratory tests will be evaluated similarly.

Efficacy Analysis. Efficacy results, including but not limited to ORR24, BORR, DOR, DCR, TTR, PFS, and OS for patients enrolled into Part A will be provided using descriptive statistics. Objective responses will be evaluated according to both RECIST v1.1 and Response Evaluation Criteria In Solid Tumors for Immunotherapeutics (iRECIST).

Note: Confirmatory scans are required for all determinations of objective response (PR or CR), Stable disease(SD) and disease progression (PD). Confirmatory scans must be performed at least 4 weeks later.

Part B follows a Simon Two-Stage mini-max design. The sample size for the first stage of Part B is 15 patients; the sample size for the second stage is 13 patients, for a total of 28 patients. Patients from Part A without a DLT, who receive the recommended Phase 2 treatment regimen and who are considered evaluable for efficacy will be included in the analysis for Part B Stage 1. For a null hypothesis ORR24 of 0.15 and an alternative hypothesis ORR24 of 0.35, the sample size of 28 subjects will provide a one-sided significance level of 5% and a power of 80%. For Stage 1, a minimum of three patients must demonstrate a response (PR or better) to proceed to the second stage. Study has passed the first stage of Simon-Two stage design. If Stages 1 and 2 are completed, a minimum of 8 patients must demonstrate a response (PR or better) to reject the null hypothesis. If a patient's responses could not be confirmed, that patient will not be included in the primary efficacy population for ORR24.

Part C is to evaluate efficacy in larger patient population.

In Keynote-158 study (pembrolizumab monotherapy in patients who have progressed with standard of care systemic therapy), ORR in total patients (i.e. regardless of PD-L1 status) and with CPS  $\geq 1$  were 12.2% and 14.6%, respectively.

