#### 10.5 Number of Patients

Maximum 60 patients are planned for recruitment to both Parts A, B and C of this study. As previously described in Section 10.2 above, minimum of 6 patients will be enrolled into Part A. The maximum number of safety evaluable patients to be enrolled into Part A is 18.

Part B of this study employs a Simon-Two Stage Design. A minimum of 15 efficacy evaluable patients (see Section 24.4), which may include some patients from Part A, will be included in the analysis for Stage 1. If 3 or more patients in Stage 1 experience objective responses (i.e., Partial Response or better), the study will move into Part B Stage 2 and an additional 13 patients

will be treated, for a total of 28 efficacy evaluable patients. Study has passed the first stage of Simon-Two stage design.

If at least 8 of the 28 subjects enrolled in Part B, experience an objective response who are considered evaluable for efficacy, it will be considered that ORR satisfies the criteria for study expansion and additional 17 subjects (at least) will be enrolled in Part C to evaluate efficacy further in larger population (N=45~60). Refer to the Section 24.3 Sample Size and Power for detailed assumptions for sample size estimation.

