#### 24.8 Final Analysis

The final analysis will be performed to report a primary CSR based on a data cut off after all 60 patients in the planned efficacy evaluation population have completed tumor assessment within 24 weeks by the investigator per RECIST v1.1

Since patient will be treated until they met one of the discontinuation criteria, some patients may still be ongoing at the time of final analysis. Therefore, a long-term follow-up study can be performed after final analysis with all available data (no cut-off date applied).

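### 60 is both the recruitment maximum, already inflated for 25% dropout, and the evaluable number that triggers the final analysis; the trigger also follows investigator rather than central assessment

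*Protocol*

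**What the plan says.** Three uses of the number 60 matter here.

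- **A maximum.** The Synopsis (Statistical Methods) states "Maximum 60 patients are planned for enrollment into this clinical trial", and Protocol 10.5 states "Maximum 60 patients are planned for recruitment to both Parts A, B and C of this study".
- **A number already inflated for loss.** Protocol 24.3 reports that "the sample size of 60 subjects was calculated considering two-sided significance level of 0.05, 97% power, and 25% dropout rate". The same sentence stands in the Synopsis, Protocol 24.1 and SAP 3.1. Section 10.5 writes the Part C population as N=45~60, whereas the Synopsis and SAP 3.1 write N=60.
- **An evaluable number.** Protocol 24.1 sets the data cut-off for the primary report after "all 60 patients in the planned efficacy evaluable population have completed tumor assessment within 24 weeks by the investigator per RECIST v1.1". Protocol 24.8 and SAP 4.3 say the same of the efficacy evaluation population.

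Two provisions could add patients. Protocol 24.4 and SAP 5.4 let non-evaluable Part B and C patients be replaced. SAP 15.1 removes patients whose best response within 24 weeks cannot be confirmed and provides for further enrolment. Neither gives a number or mentions the maximum.

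On the reader, Protocol 24.1, SAP 2.1 and SAP 15.1 base the primary endpoint on blinded independent central review (BICR). SAP 15.1 counts a response first seen within 24 weeks even when it is confirmed later.

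**The concern.** A number that allows for 25% loss cannot also be the number left after the loss. With recruitment capped at 60, a trigger of 60 evaluable patients is out of reach as soon as one patient is non-evaluable, and the plan itself budgets for about 15.

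What is at stake is the data cut-off for the primary analysis. If the written rule cannot be applied, someone must choose the cut-off, or exceed the maximum, while results accumulate in an open-label trial. Because the trigger follows the investigator's assessment, it can also be met while confirmatory scans that decide the centrally assessed endpoint are still to be taken.

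**Working it through.** **Inputs.** Null rate 12.2%, alternative 37%, two-sided 0.05, power 97%, dropout 25%, and success when the Clopper-Pearson 95% lower bound exceeds 12.2% (Protocol 24.3, SAP 3.1). Maximum 60 (Synopsis, Protocol 10.5). Trigger 60 evaluable (Protocol 24.1, 24.8, SAP 4.3).

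**1. Reproducing the plan's figure.** With n = 45, success needs at least 11 responses (lower bound for 11/45 is 12.9%).
- Power: P(X ≥ 11 | n = 45, p = 0.37) = 97.4%.
- Upper-tail error: P(X ≥ 11 | n = 45, p = 0.122) = 1.7%.
- Inflation: 45 / (1 − 0.25) = 60.

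45 is the smallest number from which exact power stays at or above 97% (96.8% at 44). It also matches Section 10.5: 28 + 17 = 45. So 60 and 97% are both correct, with 60 recruited and 45 evaluable.

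**2. If 60 meant evaluable.** Success would need at least 14 responses (lower bound 13.4%). Power would be 99.2%, not 97%, and recruitment at 25% dropout would be 60 / 0.75 = 80.

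**3. Maximum against trigger.** With 60 recruited and a non-evaluable share q, independent between patients, P(all 60 evaluable) = (1 − q)^60.
- q = 0.05: 0.95^60 = 0.046.
- q = 0.25: effectively zero, with 60 × 0.25 = 15 expected to be non-evaluable.

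**4. Other counts.** The Synopsis (Sample Size) gives approximately 46 patients for Parts A and B and at least 17 more in Part C: 46 + 17 = 63, above 60.

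**5. Why 45 should not become the new trigger.** With Bin(60, 0.75) evaluable patients the mean is 45 and the 95% range is 38 to 51, and P(fewer than 45) = 43%. A floor of 45 would often fail too. Single-stage power is 94.0% at 38 (at least 10 responses) and 98.6% at 51 (at least 12), so no floor is needed.

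**6. Scan timing.** Protocol 22.1.2 schedules imaging every 9 weeks from treatment start: 9, 18 and 27 weeks elapsed. The last scheduled scan within 24 weeks is at 18. Confirmation must come at least 4 weeks later, so at 18 + 4 = 22 weeks at the earliest, with no upper limit stated in that section. If it is taken at the next scheduled scan it falls at 27 weeks, 3 weeks past the 24-week mark, and SAP 15.1 still counts it. A trigger defined by investigator assessment within 24 weeks does not wait for that scan.

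**The case against.** **The 97% is sound.** This stands. Quoting power after allowance for dropout is conventional, and the figure reproduces. A reader might infer that 97% overstates the chance of success because Part C opens only after at least 3 of 15 and then at least 8 of 28 responses. The documents do not support replacing it. The figure sits under Part C, and Part B has its own stated 80%. Both documents say that Stage 1 has already been passed, without giving the count. The rule for opening Part C does not say that it counts the same centrally assessed 24-week responses as the final test. A combined probability would therefore need assumptions that the plan does not supply.

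**Only new Part C patients might be tested.** A reader might infer this from SAP 15.1, which does not state pooling outright. It fits poorly: a 60-subject test inside a 60-patient maximum for all parts must include earlier patients, and 28 + 17 = 45 points the same way.

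**The trigger is loose wording.** The word planned may mean everyone recruited. That may well be the intent, but three sections name the efficacy evaluable or evaluation population, which Protocol 24.4 and SAP 5.4 define by exclusion rules.

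**Replacement solves it.** Only by exceeding 60, which would contradict the Synopsis and Section 10.5.

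**Central reads will be ready.** SAP 15.1 has confirmed response determined before the analysis, so reads of images already taken can be completed. This stands. It does not help with confirmatory scans not yet acquired at the cut-off.

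**Conclusion.** The point holds as an inconsistency in the final-analysis trigger, not as an error in the sample size. The maximum of 60 and the trigger of 60 evaluable patients agree only if nobody is non-evaluable: a 4.6% chance at 5% non-evaluable, and practically none at the planned 25%, where 60 evaluable would need 80 recruited. The trigger also names the investigator although the primary endpoint is BICR-assessed, so the cut-off can fall before confirmatory scans that count are acquired. The documents do not allow an estimate of how many patients that would affect.

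This rests on reading the 25% as the non-evaluable share, which 45 / 0.75 = 60 implies, and on independence between patients for the 4.6% and the 38 to 51 range.

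A reader might also infer that type I error is inflated. It is not: single-stage upper-tail error at 12.2% is 1.7% with 45 patients and 1.2% with 60, and the Part B rules can only stop the trial.

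**What to change.** 1. **Trigger (Protocol 24.1, 24.8, SAP 4.3).** Set the cut-off when every enrolled patient (maximum 60) has completed RECIST v1.1 assessment through 24 weeks, including any pending confirmatory scan and with BICR reads available, or has stopped tumor assessment. Set no minimum evaluable number.
2. **Patient numbers (Synopsis Sample Size and Part C, Protocol 10.5, SAP 3.1).** Replace N=60 and N=45~60 with up to 60 enrolled, about 45 efficacy evaluable expected. Reconcile approximately 46 plus at least 17 with 60. State in Protocol 24.4, SAP 5.4 and SAP 15.1 that replacement and additional enrolment stay within the maximum of 60.
3. **Optional label (Synopsis, Protocol 24.1, 24.3, SAP 3.1).** Say that 97% is the single-stage power of the final test with 45 efficacy evaluable patients, pooled over the eligible Part A, B and C patients, and does not count the Part B rules.

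The cost is wording and possibly a cut-off a few weeks later. No patients are added and the test does not change.
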